Caregivers (Intervention): The intervention will be delivered in six individual hour-long sessions during three months by a trained and certified masters-level, mental health professional Program Coach, using the VAMC Memphis Caregiver Center’s national certifying procedures. These include didactic, knowledge test, and supervised role play of intervention components. The first consent and assessment visit will also be in the facility during a patient clinic visit; consent can be obtained by the Research Associate or Program Coach. At this visit, the Program Coach will also begin the Intervention process to establish rapport; subsequent caregiver REACH sessions, approximately every two weeks, will be in the facility, by telephone, or by telehealth, dependent on patient appointments and caregiver desire. All sessions will be taped and treatment fidelity will assess intervention delivery, receipt, and enactment.

STUDY FLOW CHART

First Visit Sequence

Data Collection. A trained masters-level Research Associate will collect data from Caregiver and Veteran by telephone or at clinic visits (which typically occur every three months) at baseline (first assessment and consent visit), end of intervention (3 months), and 6 months.

REACH VA MS STATEMENT OF WORK (SOW)

Task 1: Develop Manual of Operations (MOP)

Month 1

Activities

- Finalize REACH VA MS sessions format
- Finalize REACH VA MS materials
- Finalize screening materials
- Finalize data collection protocol/battery
- Develop and print brochures and posters

Products

- Program Coach notebook, topics and scripts
- Caregiver Notebook
- Screening forms and scripts
- Data collection forms, scripts and documentation
- Brochures and posters

Task 2: IRB approval

Month 1

Activities

- Develop all IRB documents

Products

- IRB study approval

Task 3: Train personnel

Month 1

Activities

- Train Program Coach and research associate

Products

- Trained and certified staff

Task 4: Recruitment and Randomization

Months 1-15

Activities

- Mail brochures

- Telephone and screen potential participants

Products

- Approximately 46 Caregivers/Veterans screened
- 25 pairs recruited

Task 5: Intervention

Months 1-20

Activities

- Schedule and provide intervention for Caregivers

Products

- Intervention sessions provided

Task 6: Data Collection/Data Entry/Cleaning

Months 1-24

Activities

- Collect Caregiver data at baseline, 3 and 6 months
- Collect Veteran data at baseline, 3, and 6 months

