During the informed consent process, the potential participant will be asked to read the consent and ask questions. A Research Associate will review key aspects of the study. Staff will question to ascertain understanding. Potential participants who are illiterate or have impaired vision will have the consent read to them. A signed informed consent is required prior to data collection. A clinic staff member not involved in the study will serve as witness.

Elements of informed consent are those mandated by the VA and will be included in the consent form. Study information includes: a statement that the study involves research, an explanation of the purposes of the research, the expected duration of the subject's participation, a description of the procedures, experimental procedures, risks or discomforts, benefits, alternatives, confidentiality, research-related injury, and voluntary participation. Additional elements appropriate to this study will also be in the form including investigator-initiated termination of participation (for example, if participation causes difficulty for the Veteran), consequences of withdrawal from study, number of subjects, future use of data (for example, the possibility of developing a data repository), payment for participating in the study as outlined in the proposal, and disclosure of results. Finally, general

research subject information will include who to contact in the event of injury or research-related questions as outlined in the proposal, and the participant's rights as a research subject.

The consent form is carbon color coded. After the participant initials and signs the form, one copy of each page is kept by the participant, and one is filed in the study office.

VETERAN AND CAREGIVER INCLUSION/EXCLUSION CRITERIA

Inclusion Criteria:

To be eligible for the proposed study:

- 1) the Veteran must be diagnosed with MS;
- 2) must be a patient in the Memphis VA Medical Center MS Clinic;
- 3) must be ambulatory; and
- 4) must have a Caregiver willing to participate.

Exclusion criteria:

- 1) Veteran not ambulatory
- 2) Caregiver not willing to participate
- 3) Veteran not willing to participate

RECRUITMENT GUIDELINES

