We will use Microsoft Access for data entry of non cost data. The Data Analyst transfers all data from paper copies to the database file. By our design, the system imposes requirements on the entry process. For example, each form must pass all logical checks such as ID validation, range and type verification, required field verification (e.g., key fields must have values), parent-child field dependencies (triggers), and duplicate detection. Secondly, each form must be verified by double entry. Lastly, all forms must be subjected to a series of consistency edits.

Data Types and Coding for Missing Data.

All data are coded in numeric form for entry and analysis (see Codebook for Measures). Missing data are entered according to the coding scheme, where -1 = missing, -2 = not applicable, -3 = don't know/unknown, -4 = refused to answer.

Editing of Data: Frequency/Range Checks, Accounting for Missing Data, Data Verification and Cleaning.

Editing of the Microsoft Access data files is accomplished with Access reports. Measurement scales are computed and frequencies obtained for study variables twice a month, to check for the presence

of out-of-range data values. When the frequency distribution for a variable indicates out-of-range values, the data search option locates these values; then, the correct score is entered from the appropriate questionnaire. The data search option is also used to locate and verify missing data of each type described above; this check of missing data takes place at the conclusion of each data entry session.

In addition to the frequency and missing-data checks described above, the values on the computer screen are double-checked against the paper forms following the entry of a participant's data. This method of verification is made relatively easy by the forms in Access. Any entry errors are corrected in the Access data file as they are encountered. Once corrections have been made in the data file, the date of verification is recorded on the cover sheet. After verification, frequency/range checks, and checks on missing data are completed for a given interview, a date for "Data Cleaned" is recorded on the cover page.

Back-Up and Disaster Recovery for Data.

All data are stored on the VA network. Data are backed up to the regional server that serves several neighboring VA facilities. The securely stored questionnaire forms also serve as backup in the event that computer files are lost or destroyed.

Disposition of Data.

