Caregiver Outcomes. Caregiver outcome variables include depression (PHQ-9) (34), anxiety (General Anxiety Disorders Scale - GAD-7) (37), with sensitivity of 0.89 and specificity of 0.82 (38), and burden (Zarit Burden Inventory) (39), which has a Cronbach's alpha of 0.85 (40). The Risk Priority Inventory RPI (41) includes data on frustrations (Caregiver Frustrations Scale) (42), vigilance, social support, physical and emotional well-being, patient safety issues, and number of and distress about patient concerns/behaviors. Patient behaviors/concerns are from the Caregiving Tasks in Multiple Sclerosis Scale (CTiMSS) (17). Other caregiver data include demographics, relationship to the Veteran, and social support. Standardized measures will be scored in accordance with published guidelines, referenced above.

Veteran Outcomes. Veteran function outcomes include the timed up and go test (TUGT) (31) and the Expanded Disability Status Scale (EDSS). The 6MW has consistently differed between persons with MS and controls and is correlated with the EDSS, Timed 25-Foot Walk Test (T25FW), and Multiple Sclerosis Walking Scale-12 (MSWS-12) scores in persons with MS (32). Other Veteran outcomes include self-efficacy, which may be a strong predictor of health status and is modifiable through encouragement (1) using the Multiple Sclerosis Self-efficacy Scale (MSSS), which has been shown to be valid, reliable, and sensitive to change over time, with a Cronbach's alpha of .81 (33), and depression (Patient Health Questionnaire - PHQ-9), which is widely used in the VA and has a Cronbach's alpha of .86 (34). Other data include MS impact on day-to-day life, which is positively correlated with caregiver activities (MS Impact Scale-29 - MSIS-29) (35), the Modified Fatigue Impact Scale (MFIS) with a Cronbach's alpha of .81 (46), and CPRS data, including type of MS and clinical severity, and Veteran service use. The standard MS clinic note template includes MS Center of Excellence data elements, including a disability clinical assessment of the patient (36). Standardized measures will be scored in accordance with published guidelines, referenced above.

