Program Evaluation. Qualitative process evaluation data will focus on content and process issues of satisfaction, benefit, utility, changes, and support to determine if the intervention process or content needs modification for use in this setting. Data will be collected from Caregivers, Veterans, and clinicians. Clinicians will help determine whether the intervention was disruptive or supportive to patient care and the clinic process and any changes needed to facilitate integration.

Data Analysis

The primary outcomes are measured for all participants at baseline, three, and six months. Data analysis will use repeated measures analysis of variance (ANOVA) to compare baseline and post-intervention follow-up (3 month and 6 month) scores. Each outcome measure will be treated as independent of the others. For continuous variables, an effect size (d) of at least 0.2 SD improvement will be considered clinically significant. Effect sizes are estimated as mean change relative to estimated population standard deviation (44). With 50 subjects and 15% attrition, we will have 80% power to reject a false null hypothesis at $\alpha = 0.05$ when effect sizes fall between 0.3 and 0.4 for depression and anxiety outcomes, and when burden outcome is 0.3, as shown below in Table 2. Cohen considered effects of this magnitude to be between small to medium (44). Recruitment of more than 50 subjects or attrition less than 15% would yield greater power than 80% or allow for detection of smaller effect sizes as statistically significant. As previously mentioned, the means, standard deviations, and effect size values below are similar to those shown in Preliminary Results.

Table 2. Caregiver Baseline Data Values Observed from Previous Studies (7, 45):

Outcome Variable	Baseline (M \pm SD)	Reliability (r)	Power	Cohen's d	n
Depression (PHQ-9) (0-27)	7.80 \pm 5.94	0.84	0.80	.3	66
				.4	38
Anxiety (GAD-7) (0-21)	8.94 \pm 5.70	0.83	0.80	.3	71
				.4	40
Burden (Zarit 12) (0-48)	17.56 \pm 9.74	0.88	0.80	.3	50
				.4	29

Note: Estimates of sample size (n) include 15% attrition of subjects during study.

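### The plan has no rule for Veterans who become unable to do the timed up and go test, so the mobility result could be biased towards improvement

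*Combined protocol and SAP*

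**What the plan says.** - **Eligibility.** The inclusion criteria require that the Veteran "must be ambulatory; and" have a participating Caregiver; non-ambulatory Veterans are excluded.
- **Outcome.** Under Outcomes, "Veteran function outcomes include the timed up and go test (TUGT) (31) and the Expanded Disability Status Scale (EDSS"). TUGT is also named in Hypothesis 1, and mobility and walking are the special focus of the intervention.
- **Analysis.** The Data Analysis section says "The primary outcomes are measured for all participants at baseline, three, and six months", and then: "Data analysis will use repeated measures analysis of variance (ANOVA) to compare baseline and post-intervention follow-up (3 month and 6 month) scores". It names no analysis set, imputation, mixed model, rank method or sensitivity analysis.
- **Missing data.** Under Data Types and Coding for Missing Data: "Missing data are entered according to the coding scheme, where -1 = missing, -2 = not applicable", followed by codes for unknown and refused. None means that the Veteran was assessed but could not do the test.
- **Size.** Task 4 of the Statement of Work gives "25 pairs recruited". The Data Analysis section says "With 50 subjects and 15% attrition, we will have 80% power to reject a false null hypothesis at" the 0.05 level. The attrition figure is used only for sample size.
- **Design.** Single-group, pre-post.

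**The concern.** A Veteran who can no longer do the TUGT has deteriorated, since all could walk at baseline, but has no time to enter. The analysis file would hold the event under a code shared with a missed or inapplicable item. A standard repeated measures ANOVA uses only people with a score at all three visits, so a Veteran unable at month 6 also loses the baseline and month 3 values. The people removed would be removed because they declined, and the mean change among the rest would shift towards improvement.

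In a two-arm trial the same loss in both arms might partly cancel. Here the whole result is the change from baseline, and with about 21 Veterans at follow-up one or two people matter. At stake is a claim of better mobility, which would feed into the future research that objective 6 of the study aims to prepare.

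**Working it through.** **Inputs from the documents.** 25 Veterans (25 pairs) and 15% attrition: 25 × 0.85 = 21.25, so about 21 at follow-up. The significance level is 0.05, and 0.2 SD counts as clinically significant. There is no TUGT figure to reproduce: Table 2 covers Caregiver depression, anxiety and burden only.

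**Assumed inputs.** TUGT lognormal with median 12 s, log SD 0.4, SD of log change 0.2, and no true change on the log scale. Between 0 and 3 of 21 Veterans become unable.

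**Check 1: simulation, 20,000 trials per setting.** Baseline is compared with one follow-up by a paired t-test. The result counted is significance in the improving direction at two-sided 0.05 (nominal 2.5%).

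| Who is lost | Scale | 0 lost | 1 | 2 | 3 |
|---|---|---|---|---|---|
| Slowest at follow-up | raw seconds | 1.4% | 2.7% | 4.1% | 5.7% |
| Largest decliners | raw seconds | 1.4% | 4.4% | 10% | 19% |
| Slowest at follow-up | log time | 2.5% | 4.0% | 5.3% | 7.4% |
| Largest decliners | log time | 2.5% | 7% | 15% | 25% |
| Unrelated to mobility change | raw seconds | about 1.5% throughout | | | |
| Unrelated to mobility change | log time | about 2.5% throughout | | | |

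The raw-seconds rate starts below 2.5% because of skewness. With no change in log time, mean seconds still rise slightly: 12·e^0.10 − 12·e^0.08 = 13.26 − 13.00 = 0.26 s.

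**Check 2: size of the shift, normal model, all 25 Veterans.** If the worst k of 25 are lost and true change is nil, the spurious improvement in baseline SD units is √(2(1−r)) × φ(z_q)/(1−q). Here q = k/25 and r is the correlation between visits. The documents give no r for TUGT, so 0.7 to 0.9 is assumed.

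Example with r = 0.84 (the value Table 2 uses for the PHQ-9) and k = 1: √0.32 = 0.566, φ(z_0.04) = 0.086, so 0.566 × 0.086/0.96 = 0.051.

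| k lost | r = 0.9 | r = 0.84 | r = 0.7 |
|---|---|---|---|
| 1 | 0.040 | 0.051 | 0.070 |
| 2 | 0.072 | 0.091 | 0.125 |
| 3 | 0.102 | 0.129 | 0.176 |
| 4 | 0.130 | 0.164 | 0.224 |

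The plan's 0.2 SD threshold is passed only at k = 4 with r = 0.7.

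**Check 3: the planned method and the remedy** (r = 0.84, 25 Veterans, 4,000 trials per setting, largest decliners affected).

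| k affected | 0 | 1 | 2 | 3 | 4 |
|---|---|---|---|---|---|
| Three-visit ANOVA rejects, either direction (nominal 5%) | 5.3% | 6.9% | 11.8% | 16.8% | 23.4% |
| Signed-rank, affected kept at worst rank: false improvement | 2.6% | 1.7% | 1.2% | 0.3% | 0.0% |

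The worst-rank analysis removes the bias and becomes conservative as more Veterans are unable.

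**The case against.** **Exclusion is inferred.** No sentence says that untestable Veterans are dropped or that seconds are analysed untransformed. The plan speaks of scores, says that standardized measures follow published scoring guidelines, and refers to an Interviewer Instruction Manual that is not reproduced. This stands, and is why the point says *could*. A form instruction would still not supply the analysis rule that the Data Analysis section lacks.

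**The number affected is unknown.** The background text gives only the long-run share of patients with mobility problems, over 10 to 15 years. Three of 21 would be about 14% in six months. The 21 is also already net of attrition, so some losses may be counted twice. This stands.

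**The largest-decliner scenario is extreme.** Under the assumed values the typical largest decliner goes from 12 s to about 17 s and would still give a time, so that scenario truncates ordinary variation. It marks an upper end. A reader might take 25% as the expected error rate. The documents do not support that: it needs log time and the loss of exactly the three largest decliners.

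**Decline is recorded elsewhere.** The EDSS is scored by a physician at a clinic examination and can still register loss of walking; MSIS-29 and clinical severity are also collected. A reader might extend the bias to EDSS, or cite its ordinal scale. Neither follows: EDSS does not depend on a TUGT time, and its scale does not bear on this loss. But the TUGT result itself would remain biased.

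**Stakes are limited.** This is a feasibility study, TUGT is not named as primary, and power is stated only for Caregiver outcomes. That limits the severity but does not remove a gap that favours the hoped-for result.

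**Conclusion.** The point holds in limited form. The documents establish that all Veterans walk at entry, that TUGT is a hypothesis-bearing outcome, that no code or rule covers inability to do it, and that the only named analysis needs a score at each visit. The direction of the possible bias is therefore clear: towards improvement.

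Its size is not established. It is nil if nobody becomes unable, or if inability is unrelated to mobility change. One Veteran lost of 25 shifts the mean by about 0.04 to 0.07 SD, well under the plan's 0.2 SD. With three lost of 21, false improvement lies between 5.7% and 19% on raw seconds, and up to 25% on log time, if those lost are the slowest or the largest decliners. All of this rests on assumed TUGT values and on listwise exclusion. A reader might infer that the mobility result will be invalid; the documents do not show that. The change is worth making before data are seen, because it is cheap and the sample is small.

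**What to change.** 1. Add a TUGT code for *assessed, unable for mobility reasons*, separate from missing, not applicable, unknown and refused.
2. Report the number so coded at baseline, 3 and 6 months, even if it is zero, and separately the number missing for other reasons.
3. Add to the Data Analysis section a pre-specified Wilcoxon signed-rank analysis of TUGT change from baseline, with these Veterans at the worst rank. Report it beside the ANOVA, and require the two to agree before TUGT improvement is claimed.
4. Optionally, add speed (1/seconds) with 0 for unable as a further check. It should not replace the main analysis: under the assumed values, with nobody unable, it gave 4.0% false improvement against 1.4% for raw seconds.

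**Cost.** One form code and a few lines of text. The rank result is not in seconds, so median seconds should be reported too, and it is conservative when several Veterans are unable. A Veteran who does not attend at all remains missing, so the code does not cover every loss linked to decline.

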 End of Intervention (3 months) and 6 month interview completed outside of -14/+14 day window
 Caregiver does not complete all 6 sessions within 4 1/2 months

RECRUITMENT

Caregivers will be recruited from the MS clinic and inpatient unit as Veterans are admitted or seen. We are requesting a waiver of informed consent and HIPAA authorization for recruitment purposes only, as a method of recruiting Veterans who have been diagnosed with MS, prior to participation in the study. Privacy risks to research subjects will be minimal. We will mail brochures to eligible Veterans. Veterans and/or Caregivers may contact us if they are interested in participating. If we do not hear from the Veteran and/or Caregiver in a reasonable amount of time after mailing the brochures, we will telephone the Veteran to give him/her more information about the study. The MS Clinic meets one day a week and study staff will be present to provide information and to screen Caregivers and Veterans. However, Veterans with MS are only seen in the MS clinic every three to six months, thereby potentially missing the enrollment period. Brochures will be mailed to all eligible participants. Brochures will also be strategically positioned around the hospital as well as in the MS clinic. Clinicians in the MS clinic will aid in the identification of eligible Veterans. Full informed consent and HIPAA authorization will be collected after screening as part of study enrollment. Our consent process for Caregivers and Veterans is overseen by the VAMC Memphis IRB and Research and Development Committee.

Screening. Participants must give permission to the Research Associate to be screened after hearing a study description that includes information about the research study and the screening process itself. Research study information includes a statement of the research (purpose, procedures), reasonably expected benefits to subjects or others, and costs. Screening process information includes duration of screening, alternatives, extent of confidentiality, and authorization for release of protected health information for research purposes.

Caregiver Consent and Veteran Consent. After screening, consent forms are provided to the Caregiver and Veteran participant. All participants must give written informed consent before becoming study participants and both Caregiver and Veteran must agree for the Caregiver to participate.

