Paper forms of the research records are kept in secure locked files in the project office. Electronic data is stored on a VA server folder that only local VAMC project research staff can access. After the study is completed, paper data will be stored with other completed research studies in a secured storage area. Records will be maintained and/or destroyed in accordance with the VA Records Control Schedule (RCS 10-1). For electronic information, as stated in the consent form, research information is analyzed for many years after a study, therefore, no specific date can be provided when this information will be destroyed or no longer used.

SCHEDULE OF DATA COLLECTION ASSESSMENTS

Time Frame for Caregiver		
Baseline (Face to Face) After consent signed and before intervention	Second (Telephone or Face to Face) 3 months (+/-14 days)	Third (Telephone or Face to Face) 6 months (+/-14 days)
X	X	X

Time Frame for Veteran		
Baseline (Face to Face) After consent signed	Second (Face to Face) 3 months (+/-14 days)	Third (Face to Face) 6 months (+/-14 days)
X	X	X

MEASURES

Data collection will occur at baseline, End of Intervention (3 months), and 6 months either face to face or by telephone. Data collection will take 30 minutes to an hour, based on face-to-face and telephone data collection in our work with OEF/OIF spouses and soldiers, and stressed caregivers, using the same and similar instruments (Table 3). We have used telephone and face to face batteries of similar length for older caregivers, who have not reported difficulty with these methods of data collection. If interviews completed over the phone, we will send response cards to the participant to make answering more efficient. The same RA will perform all data collection for a participant.

Measures were specifically chosen 1) to capture the mechanisms of action related to the theoretical model for individual stress process, and 2) to map onto measures being used by Multiple Sclerosis clinicians and researchers to provide maximum utility and generalizability for the study results.

If the Veteran/Caregiver team withdraws from the study, we will try to complete an abbreviated program evaluation to determine the reason for withdrawal.

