The Research Associate will read the Interviewer Instruction Manual (QxQs) in Manual of Operations Volume II. The Interviewer Instruction Manual will provide general guidelines and specific, question-by-question instructions for completing the REACH VA MS interviews and forms.

MEASURES AND TIME

CAREGIVER

Category	Name of Measure/Form	Citation/Source	Items	When
Demographic information	Participant demographics	various sources	15	Study entry
Health and health services		various sources	17	Study entry Follow up
Depression	Patient Health Questionnaire (PHQ-9)	(Kroenke et al., 2001)	9	Study entry Follow up
Anxiety	Generalized Anxiety Disorder (GAD-7)	(Spitzer et al., 2006)	7	Study entry Follow up
Social Support	Social Support	REACH II	10	Study entry Follow up
Burden	Zarit Burden Interview	(Bedard et al., 2001)	12	Study entry Follow up
Caregiving Tasks	Caregiving Tasks in Multiple Sclerosis Scale (CTiMSS)	(Pakenham, 2007)	24	Study entry Follow up
Risk Assessment	Risk Priority Inventory	Various sources	57	Study entry Follow up

VETERAN

Category	Name of Measure/Form	Citation/Source	Items	When
Demographic information	Participant demographics	various sources	11	Study entry
Health and health services		various sources	6	Study entry Follow up
Depression	Patient Health Questionnaire (PHQ-9)	(Kroenke et al., 2001)	9	Study entry Follow up
Impact on daily life	MS Impact Scale (MSIS-29)	(Riazi et al., 2002)	29	Study entry Follow up
Mobility	Timed Up and Go Test (TUGT)	various sources		Study entry Follow up
Self-Efficacy	MS Self-Efficacy Scale (MSSS)	(Rigby et al., 2003)	14	Study entry Follow up
Fatigue	Modified Fatigue Impact Scale (MFIS)	(Fisk et al., 1994)	21	Study entry Follow up
*Mobility/Neurological exam	Expanded Disability Status Scale (EDSS)	(Kurtzke, 1983)		Study entry Follow up

*Neurological exam completed by physician during clinic appointment.

OUTCOMES

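### Repeated measures ANOVA over three visits has no rule for a missing visit; a mixed model on all available visits (or, failing that, stated pairwise comparisons) would avoid discarding collected scores

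*Combined protocol and SAP*

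**What the plan says.** The Data Analysis section gives one method for every outcome: "Data analysis will use repeated measures analysis of variance (ANOVA) to compare baseline and post-intervention follow-up (3 month and 6 month) scores". Outcomes are due at baseline, 3 and 6 months.

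Attrition appears only as an allowance in the sample size. The note to Table 2 reads "Estimates of sample size (n) include 15% attrition of subjects during study". Task 4 of the Statement of Work sets the size of the study: "25 pairs recruited".

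Other sections touch on missing information, but none gives an analysis rule:
- Data Types and Coding for Missing Data gives numeric entry codes.
- Retention Procedures covers reminders, rescheduling and tracing.
- Withdrawal from the Protocol covers a discontinuation questionnaire, and lets one member of a pair continue without the other.
- Screening and Consent logs out-of-window follow-ups as protocol variations, without saying whether those scores are analysed.

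Part of the document was not available for this review, so a rule placed there could not be checked.

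**The concern.** Classical repeated measures ANOVA needs a complete row for each participant. If it is run that way here, two kinds of participant lose valid data:

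- someone seen at baseline and 3 months but lost by 6 months disappears from the 3-month comparison;
- someone with baseline and 6-month scores but no 3-month score disappears from both comparisons.

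Two analysts could follow the same sentence and analyse different people. With 25 caregivers and 25 Veterans, each discarded participant visibly widens an already wide interval. The 15% allowance does not clearly cover this, because it is described as loss during the study and not as a single missed score in someone who stays.

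**Working it through.** **Inputs.** From the documents: 25 pairs (Statement of Work, Task 4); 15% attrition, alpha 0.05, d = 0.3 and a 0.2 SD clinical threshold (Data Analysis); r = 0.84 for caregiver PHQ-9 (Table 2). Assumed: two-sided tests, since sidedness is not stated; r = 0.7 and 0.6 as lower values, since no correlation is given for Veteran outcomes; equal correlation between visits.

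**1. Table 2.** n = 2 × 2(1 − r)(1.960 + 0.842)² / d². For PHQ-9 at d = 0.3: 4 × 0.16 × 7.85 / 0.09 = 55.8, so 56; 56 / 0.85 = 65.9, so 66, as printed. The same steps give the other five entries (38; 71 and 40; 50 and 29). This is a per-group formula for comparing change between two groups, which is a separate matter. Here it shows that r acts as the correlation between visits and that the 15% is only an inflation of n.

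**2. Completers.** 25 × 0.85 = 21.25, so about 21 complete and 4 lost. The documents do not say when the loss occurs.

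**3. All loss after month 3.** The variance of a mean change is 2σ²(1 − r)/n. The classical ANOVA uses 21 at 3 months although 25 have both scores, so the ratio is 25/21 = 1.19 at any r. Paired t power (noncentral t, dz = d/√(2(1 − r))) at d = 0.3:

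| r | n = 25 | n = 21 |
|---|---|---|
| 0.84 | 0.72 | 0.64 |
| 0.7 | 0.46 | 0.39 |
| 0.6 | 0.36 | 0.31 |

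At r = 0.84 the 95% CI half-width is 2.064 × √(0.32/25) = 0.23 SD with 25, and 2.086 × √(0.32/21) = 0.26 SD with 21. At 6 months the theoretical ratio is about 1.05. A simulation that estimated the covariance showed 1.00 when dropout was unrelated to the scores, so no 6-month gain should be counted on.

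**4. All loss before month 3.** The same 21 people have both follow-ups. The ratio is about 1.0.

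**5. Illustration: 4 of the 21 retained miss month 3 (assumed).** That leaves 17 complete, 4 with baseline and month 6, and 4 with baseline only. The all-available variance comes from inverting the summed information (for each pattern, its n times the inverse of its covariance matrix).

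| r | Complete-case / all-available, 3 months | Same, 6 months |
|---|---|---|
| 0.84 | 1.07 | 1.25 |
| 0.7 | 1.08 | 1.27 |
| 0.6 | 1.09 | 1.28 |

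As reductions in variance, the 6-month figures are 1 − 1/1.25 = 20% to 1 − 1/1.28 = 22%. The 3-month figures are roughly 6 to 9%; no model recreates a score that was not measured.

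**6. Pairwise comparison in the same illustration.** At 6 months it uses 21, so complete-case over pairwise is 21/17 = 1.235. The mixed model is ahead of pairwise by 1.25/1.235 = 1.01 to about 1.03. At 3 months pairwise uses the same 17, so the mixed model is 7 to 9% ahead. In step 3, pairwise at 3 months equals the mixed model.

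**7. Bias.** In simulations with dropout depending on an observed score (assumed log-odds slope of 1 per SD), the complete-case change was off by about 0.02 to 0.03 SD in most affected contrasts at r = 0.84, against a true 0.30. With 6-month dropout driven by the 3-month score, the 3-month bias reached 0.06 SD at r = 0.6. The all-visits estimate stayed within about 0.01 SD at r = 0.84.

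**The case against.** **The plan never says it will delete incomplete cases.** A reader might infer that it does. The documents do not support that: the sentence can be read as baseline against each follow-up separately, which would avoid both losses. This stands. The defect is silence combined with a method whose classical form discards data, not a stated decision to discard.

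**One added sentence does most of the work.** Step 6 bears this out. Pairwise comparison is 0 to 9% less efficient than the mixed model, depending on contrast and pattern. The mixed model also uses the baselines of people lost early. In the simulation where early loss depended on baseline, the complete-case estimate (there identical to pairwise) kept its 0.02 to 0.03 SD bias and the mixed model did not. It is the better choice, but not by much.

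**A reader might infer that many Veterans will lack a 3-month EDSS.** The measures table says "Neurological exam completed by physician during clinic appointment", and the Recruitment section says "However, Veterans with MS are only seen in the MS clinic every three to six months". The documents do not support a rate. The Recruitment sentence explains why the enrolment period might be missed. The Research Methods section says the Research Associate "will collect data from Caregiver and Veteran by telephone or at clinic visits (which typically occur every three months". The Veteran schedule lists "Second (Face to Face) 3 months (+/-14 days", and Retention Procedures adds reminders and rescheduling. A Veteran seen late gives a late score, not a missing one. The Measures text, "Data collection will occur at baseline, End of Intervention (3 months), and 6 months either face to face or by telephone", covers caregivers as well and can be squared with a face-to-face Veteran schedule. These passages, and the interview labelled 3-month that may follow sessions running to 4½ months, should be reconciled as a separate matter. They are not evidence of how many scores will be missing.

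**This is a feasibility study.** Its first objective is integration into a clinic. That limits the seriousness, but the plan also tests two hypotheses of significant improvement, so the analysis set matters.

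**Conclusion.** The concern holds in limited form. The plan names a three-visit ANOVA, expects attrition and gives no missing-visit rule in the text available. The cost depends on when scores are lost: about 1.19 times the variance at 3 months if all loss follows month 3, almost none if it precedes month 3, and 1.25 to 1.28 times at 6 months in an assumed case where 4 of 21 retained participants skip month 3. The documents give no frequency for such misses.

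The power figures use the caregiver PHQ-9 correlation, or assumed lower ones, and a two-sided paired t test. Applying them to Veteran outcomes is an assumption. Bias is secondary.

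A reader might infer that a mixed model would make the study adequately powered. It would not: with all 25 analysed, power at d = 0.3 is 0.72 at r = 0.84 and 0.36 at r = 0.6. The change only stops collected data being thrown away. It should be made because it is cheap, but it is not a fatal flaw. Confidence is medium.

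**What to change.** In Data Analysis, replace the ANOVA sentence with text to this effect:

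> Each continuous outcome will be analysed with a likelihood-based linear mixed model for repeated measures, with visit as a categorical factor, unstructured covariance and small-sample degrees of freedom, using all available visits of every participant with a baseline score. The prespecified contrasts are baseline to 3 months and baseline to 6 months, each with a 95% confidence interval. The number observed at each visit will be reported for each outcome. Because EDSS is ordinal, a Wilcoxon signed-rank test of change at each follow-up will be a sensitivity analysis.

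If ANOVA is kept, state that each follow-up is compared with baseline separately in everyone who has both scores.

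**Cost.** No new data and no change to visits. It takes slightly more analysis work and mixed-model software, and the mixed model relies on data being missing at random.
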